CLE is typically categorized as acute (ACLE), subacute CLE (SCLE), and chronic (CCLE). ACLE develops in nearly one half of patients with SLE, but most or all people with ACLE have SLE. Also known as "malar rash" or "butterfly rash", ACLE is characterized by erythema distributed over the cheeks and nasal bridge of the face.¹ SCLE is less common but may appear as round, scaly lesions with central clearing. Discoid Lupus Erythematosus (DLE), a form of CCLE, is one of the most common forms of cutaneous lupus and can appear as erythematous and hyper- and hypopigmented lesions with telangiectasias. Frequently these lesions lead to scarring and can be permanently disfiguring.

First line management of CLE involves photo protection along with topical corticosteroids and possibly systemic agents. Other treatments include intralesional steroids and/or topical calcineurin inhibitors.¹ Both topical and systemic medications carry a wide range of adverse and toxic effects.³⁻⁵

Though not well-known, laser therapy has been shown to be effective in the treatment of cutaneous lupus.⁶⁻⁸ Many providers may be wary of using lasers on these patients given the ability of ultraviolet light to exacerbate or flare SLE.^{9,10} It is believed that by targeting the superficial vasculature the lasers are able to attenuate the inflammatory response seen in the skin.¹¹

The 585 nm, 595 nm and 1064 nm wavelength lasers have all been shown to be effective in the treatments of cutaneous lupus.^{6-8,12} Given their ability to target vasculature, these lasers are currently used to treat vascular lesions and inflammatory conditions such as port wine stains, telangiectasias, hemangiomas, rosacea, and scars.^{13,14}

Lasers utilizing the 532nm wavelength also have been shown to treat the same vascular and inflammatory conditions as the above mentioned wavelengths. This is due to the fact that the 532nm laser targets the same chromophore of oxyhemoglobin.^{15,16}

Therefore, given that the 532nm has very similar properties and same mechanism of action as other vascular lasers shown to be effective at treating cutaneous lupus it would be reasonable to consider that the 532nm laser could be utilized to treat cutaneous lupus as well.¹⁷

However, since the 532 nm should be used with caution in darker skin people and SLE is 2 to 4 times higher in African-American women than Caucasian women, utilizing only the 532nm would limit the applicability of the proposed study.^{14,18}

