 - Unable to read and speak English since consent will only be available in English

[figure not shown]
- d) Study Endpoints
 - Primary endpoints: Participation in the study will end after the third visit.
 - Primary safety endpoints: none
 - Secondary safety endpoints:
 - Adverse reaction to the laser treatment such as blister, ulceration, and scarring.
 - Adverse reaction to the topical steroid such as atrophy, telangiectasias or striae.
 - Intolerance to pain of laser procedure.

- e) Study Timelines
 - Each participant will be in the study for a maximum of 8 weeks. Participants will receive 2 laser treatments. The laser treatments will be spaced 4 weeks apart between visit 1 and visit 2. Finally, 4 weeks after visit 2, the participants will be followed up during visit 3.

 - The duration expected for all study participants to be recruited is estimated to be 28 weeks.

 - The study will end when the last participant has completed the 2 laser treatments and follow up. The goal is to conclude the data collection by October 31, 2018 and complete primary analysis by December 31, 2018.

- f) Procedures involved in the Human Research.
- This study will be a randomized prospective study. All study lesions will receive topical treatment. One lesion will only receive topical treatment to serve as a control, and up to 2 others will also receive laser treatment in addition to the topical treatment.
 - Standard of care treatment will be a topical corticosteroid as follows:
 - Discoid lupus lesions: Betamethasone dipropionate augmented 0.05% cream twice a day as needed
 - Non-discoid cutaneous lupus lesions: Triamcinolone acetonide 0.1% cream twice a day as needed
 - Laser treatment will be randomized based upon the participant Fitzpatrick Skin Type as follows:
 - Fitzpatrick Skin Types I – III:
 - § Treatment lesion will be treated with 532nm laser or 1064nm laser
 - § 50:50 randomization for laser used (determined by coin flip)
 - § If the participants have an additional lesion then this will be treated with the laser not used for the treatment lesion
 - Fitzpatrick Skin Types IV - VI
 - § Treatment lesion will only be treated with the 1064nm laser. This is because the 532 nm wavelength is absorbed easily by melanin and thus can cause skin pigmentation abnormalities when used with darker skin participants.
 - Laser treatment system details and parameters:

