 - The Excel V laser system manufactured by Cutera (Brisbane, CA) will be used to administer all laser treatments. This laser has the capability of emitting both 532nm and 1064nm wavelengths.
 - Treatments with the 532nm wavelength will utilize parameters in the following ranges:
 - § Spot size: 1-12mm
 - § Fluence: 5-12 J/cm²
 - § Pulse Duration: 3-15ms
 - § Temperature: 5-10°C
 - Treatments with the 1064nm wavelength will utilize parameters in the following ranges:
 - § Spot size: 1-12mm
 - § Fluence: 10-60 J/cm²
 - § Pulse Duration: 10-60ms
 - § Temperature: 5-10°C
 - Note: If the lesions are ill-defined such as those of ACLE and SCLE then a lesion will be defined as a 2cm² within the involved area.

- Timeline:

Pre-Week 0: Screening Visit

- Screening: participant will be screened for inclusion and exclusion criteria, including urine pregnancy test if necessary.

Week 0: Visit 1

- Baseline lesion assessment, lesion selection, randomization and treatment 1 will occur.

Week 4: Visit 2

- Follow up lesion assessment
- Treatment 2

Week 8: Visit 3

- Final lesion assessment

- Lesion assessment:

Limited CLASI:

The classification of cutaneous lupus will be recorded for each participant.

A “limited” CLASI scoring system will be used, subdivided into an “active” and “damage” components.

The limited active CLASI for a lesion will include the following:

- Erythema (ranging from 0 = absent to 3 = dark red/purple)
- Scale/Hypertrophy (ranging from 0 = absent to 2 = verrucous/ hypertrophic)
- The addition of these scores result in a total limited active CLASI score of the studied lesion, ranging from 0 to 5.

The limited damage CLASI for a lesion will include the following:

- Dyspigmentation (0 = absent or 1 = present)
- Scarring/Atrophy/Panniculitis (ranging from 0 = absent to 2 = severely atrophic scarring or panniculitis).
- The addition of these scores result in a maximum damage score of 3.

The total limited CLASI reflects the sum of both active and damage CLASI, resulting in a score ranging from 0 to 8.

Photographs will be taken of all study lesions during every assessment.

All participants will be evaluated by [name] at baseline and at subsequent visits.

All participants will be evaluated via photograph by [name] at baseline and subsequent visits. [name] will be blinded to the treatment type so as to be an independent observer. He will utilize the “Independent Observer Survey” to document his assessments.

Visual Satisfaction of Appearance:

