g) Data and specimen management

There will be no specimen collection, and thus there will be no management of physical specimens.

If a participant withdraws from the study, the reason for the withdrawal will be noted but data collected up to that point will be used.

All data will be collected on the survey documents (see attached documents “Survey” and “Independent Observer Survey”). These survey documents will be stored in regulatory binder in a locked drawer in locked room at UCF Health. This will only be accessible only to the principal investigator and co-principal investigators. These survey documents will then be used to transfer the data to the REDCap database, afterwards they will be disposed of in HIPAA-compliant shred bin.

Photographs of study lesions will be stored directly in the EHR.

The data will be analyzed for significant differences with aid of a statistician. A significance level of 0.05 will be used for statistical hypothesis testing. The results of the data analysis will be graphed for each parameter.

h) Provisions to monitor the data for the safety of participants

The principal investigator and statistician will periodically review cumulative CLASI scores and adverse effect data every 10 patients.

If the change in the active CLASI score for the treatment lesion is 3 points higher than the change in the active CLASI score for control lesions with $p < 0.05$ then the study will be suspended immediately.

If participants have ulceration or scarring attributable to the laser treatment as an adverse effect with $p < 0.05$ then the study will be suspended immediately.

i) Withdrawal of participants

Participants will be withdrawn from the research without their consent if they become intolerant to the laser treatments and/or the investigators determine that they are too nervous, anxious to continue.

Participants may terminate their participation in the research study at any time by informing a member of the research team. If the participant declines any further laser treatments he or she may still participate in the study with follow up assessments being completed.

If participants miss study Visit 2, the researchers will attempt to reach the participant to reschedule. If the participant is unable to reschedule within 2 weeks of the missed appointment then the participant will forego the 2nd treatment and attempted to be scheduled for Visit 3.

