Topical corticosteroid associated risks²⁰:

- Atrophy
- Telangiectasias
- Striae
- Perioral dermatitis
- Hypertrichosis
- Folliculitis
- Note: All risks are approximately <5%²¹

9) Potential direct benefits to participants

While there are no guarantees that participants will receive any benefits from their participation in this study, potential benefits include quicker improvement of cutaneous lupus lesions less scarring than standard of care, and topical treatment at no cost for cutaneous lupus for duration of study participation.

10) Provisions to protect the privacy interests of participants

Participants will be seen and treated in the same manner as patients in the UCF Health clinic. In the clinic, efforts are made to protect patients' privacy whenever possible as per HIPAA guidelines.

11) Provisions to maintain the confidentiality of data

Data will be stored in the secure HIPAA-compliant database called REDCap. Unique identifiers will be created using sequential numbers (i.e. 1, 2, 4 etc.).

No data collection instrument in REDCap will contain identifying information

A screening and enrollment log (see attached document “Screening and Enrollment Log”) will be stored in a regulatory binder in a locked drawer in a locked room at UCF Health. Only [name] will have access to this locked drawer.

A subject ID assignment list (see attached document “Subject ID Assignment List”) that links the subject name and contact information with their unique identifier will be stored in a separate folder in locked drawer in a locked room at UCF Health. Only [name] will have access to this locked drawer.

Identifying information such as the “Subject ID Assignment List” will only be accessed by the PI and co-PIs for initial entry. It is possible the identifiable information may be referenced if questionable data are detected during data analysis (e.g.: number out of range, missing data).

The “Screening and Enrollment Log” and the “Subject ID assignment List” will both be disposed of in a HIPAA-compliant shred bin at the completion of the study.

Informed consents and HIPAA authorizations will be stored in locked drawer in a locked room at UCF Health and kept for a minimum of six years after the conclusion of the study (per UCF data retention policies.)

Only de-identified data will be used and exported for analysis.

De-identified data will be stored for a minimum of five years after the conclusion of the study (per UCF data retention policies).

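### The scarring safety endpoint and suspension rule count scars only when attributed to laser, in a disease that itself scars, and no laser-versus-control comparison of scarring is specified

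*Combined protocol and SAP*

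**What the plan says.** All references are to the combined protocol and SAP.

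- **7(d) Study Endpoints.** "Primary safety endpoints: none". Scarring enters as a secondary safety endpoint, in the form "Adverse reaction to the laser treatment such as blister, ulceration, and scarring".
- **7(h), safety monitoring.** One suspension rule begins "If participants have ulceration or scarring attributable to the laser treatment as an adverse effect" and adds a p-value below 0.05. It names no comparator, test or method of attribution. The other begins "If the change in the active CLASI score for the treatment lesion is 3 points higher", so it uses only the active score (erythema and scale). The same section has CLASI scores and adverse effects reviewed every 10 patients.
- **4) Background.** Of discoid lupus: "Frequently these lesions lead to scarring and can be permanently disfiguring".
- **9) Potential direct benefits.** The possible benefits include "quicker improvement of cutaneous lupus lesions less scarring than standard of care".
- **7(f) Procedures.** Each participant has one steroid-only control lesion and up to two laser lesions. The limited damage CLASI includes "Scarring/Atrophy/Panniculitis (ranging from 0 = absent to 2 = severely atrophic scarring or panniculitis". All study lesions are photographed at every assessment, and the photograph assessor "will be blinded to the treatment type so as to be an independent observer". Scarring is also on a list of adverse effects to be monitored, with no attribution condition.
- **8) Risks.** Scarring from laser is listed under risks below 1%.

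**The concern.** In this trial scarring is at once a possible laser harm, a disease outcome and something the laser might reduce. An endpoint that counts only scars judged to be caused by laser needs someone to decide, lesion by lesion, whether laser or lupus was responsible. The plan does not say who decides, by what criteria, or whether blinded.

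A control lesion receives no laser and so can never have a laser-attributed scar. Its count is zero by definition and says nothing about how often lupus lesions scar under steroid alone. An attributed count also cannot fall below zero, so it cannot show the reduction that section 9 mentions. The reported scarring rate would depend on the attribution habit of the assessor, and the p-value in the 7(h) rule has no stated reference.

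The plan already provides for lesion-level scores and a control lesion in the same participant, which would allow a comparison that needs no attribution.

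**Working it through.** The plan gives no scarring rate for the disease and no figure for this comparison, so there is nothing of its own to reproduce. The steps below show how the definition behaves under assumed rates.

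**1. Inputs.** From the documents: 25 participants (7(a)), one control lesion each (7(f)) and a stated laser scarring risk below 1% (section 8). Assumed: an 8-week disease scarring rate *d* of 5% to 20%, an added laser rate *L* of 0% to 10%, independence of the two causes, and one laser lesion per participant. The last is a simplification, since 7(f) allows two.

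**2. Range of the attributed count.** The proportion of laser lesions with new scarring is 1 − (1 − *d*)(1 − *L*). Attribution can report anything from none to all of these. The excess is the laser count minus the control count.

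| *d* | *L* | Laser lesions scarred | Expected in 25, laser | Expected in 25, control | Attributed count can be | Excess |
|---|---|---|---|---|---|---|
| 5% | 0% | 5% | 1.25 | 1.25 | 0 to 1.25 | 0 |
| 10% | 0% | 10% | 2.5 | 2.5 | 0 to 2.5 | 0 |
| 20% | 0% | 20% | 5.0 | 5.0 | 0 to 5.0 | 0 |
| 10% | 5% | 14.5% | 3.6 | 2.5 | 0 to 3.6 | 1.1 |
| 20% | 5% | 24% | 6.0 | 5.0 | 0 to 6.0 | 1.0 |
| 10% | 10% | 19% | 4.75 | 2.5 | 0 to 4.75 | 2.25 |

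Last row: 1 − 0.90 × 0.90 = 0.19, and 0.19 − 0.10 = 0.09. The ends of each range are the extremes of attributing no scar or every scar. They are bounds, not forecasts.

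**3. Precision of a laser-minus-control difference.** For 19% against 10% in 25 pairs, with lesions independent within participant, the standard error is √[(0.19 × 0.81 + 0.10 × 0.90)/25] = √(0.2439/25) = 0.099. The approximate 95% interval is 0.09 ± 1.96 × 0.099, or about −10 to +28 points. Splitting by wavelength leaves fewer pairs and a wider interval, particularly for 532nm, which is used only in skin types I–III.

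**4. Why not a test.** A two-sided exact McNemar test needs at least six participants with scarring on the laser lesion only and none on the control only: 2 × 0.5⁶ = 0.031, whereas 2 × 0.5⁵ = 0.0625. At *d* = 10% and *L* = 10%, power with 25 pairs is about 6%.

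**5. What 25 participants can say about a risk below 1%.** If 0 of 25 scar, the two-sided upper 95% limit is 1 − 0.025^(1/25) = 13.7%. At a true risk of 1%, the chance of seeing any laser scar is 1 − 0.99²⁵ = 22%, so it is at most 22% at the stated risk.

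**The case against.** A reader might infer that scarring is recorded nowhere unless it is blamed on the laser, and that the scarring score plays no part in safety. The documents support neither. The adverse-effect list in 7(f) includes scarring without attribution. The review in 7(h) covers CLASI scores without limiting them to the active part, and the total limited CLASI includes damage. Section 7(g) also says that each parameter will be graphed. What is missing is narrower: a safety endpoint or threshold that uses the item, and a specified comparison with control.

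It is also tempting to say that a blinded scarring score already exists for every lesion. That is a fair inference, but the Independent Observer Survey is not among the documents, and blinding to treatment type does not settle whether laser versus no laser is masked.

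Other objections stand as limits on the remedy:

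- The coin flip in 7(f) chooses the laser, in skin types I–III. Nothing says that the control lesion is chosen at random, so a difference could reflect lesion selection.
- The item merges scarring with atrophy and panniculitis, and atrophy is a listed steroid reaction in 7(d). All study lesions receive steroid, which helps the comparison, but a one-point rise is not specifically a scar.
- The section 4 statement concerns discoid lupus, while 7(f) also admits acute and subacute lesions. The assumed rates need not apply to that mix, and a 10% laser risk is at least ten times the stated one.
- Follow-up ends 4 weeks after the last planned laser treatment.

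Finally, the analysis plan is brief throughout, so this could be called one instance of a general lack of detail. That does not remove the point: here the plan does state a definition, and the definition itself cannot separate the two causes.

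**Conclusion.** The concern holds for the scarring endpoint in 7(d) and the scarring suspension rule in 7(h). Both depend on an undefined attribution to laser in a disease that scars, so attributed events alone can overstate or understate laser scarring at any non-zero disease rate. The size of the error cannot be given, because the documents contain no disease scarring rate; the table in the working is illustration only.

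A within-participant comparison would be more informative, but at this sample size it supports only a descriptive estimate. It can neither confirm the risk below 1% in section 8 nor establish the benefit in section 9. This is a cheap improvement worth making. It does not show that the trial would misreport scarring.

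**What to change.** Keep investigator attribution as a listing, and add one descriptive table:

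- **Outcome:** for every study lesion, control included, whether the scarring/atrophy/panniculitis item rose by at least 1 point from that lesion's own Visit 1 score.
- **Source:** the blinded photograph rating, if the Independent Observer Survey records this item and laser versus no laser is masked. Otherwise use the in-person rating, labelled unblinded.
- **Report:** laser versus control within participant, separately for 532nm and 1064nm, as a risk difference with a 95% interval and no hypothesis test. Give the number of lesions already at 2 at Visit 1, which cannot worsen.
- **Limits to state beside the table:** the merged item, the control lesion not stated to be randomly chosen, the 4-week follow-up after the last laser treatment, and the inability of about 25 participants to verify a risk below 1%.

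The investigators should also reconcile the scarring wording in 7(d), the 7(f) adverse-effect list and the 7(h) suspension rule, including what its p-value is compared with. No clinical rule is proposed here.

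The cost is a paragraph of analysis text and one table from planned scores, with no change to treatment or visits. Disease scarring counted on both lesions adds some noise.

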Therefore, we are proposing investigating the use a 1064nm laser as well in treating cutaneous lupus as this wavelength is safe on people of all skin types.⁹ The 1064nm laser has previously been shown to be effective in cutaneous lupus though further studies are needed to confirm the preliminary findings and better characterize the effectiveness.¹¹

When compared to available topical and systemic therapies, laser therapy generally has been shown to have minimal side effects. The most common adverse effect is bruising

but that usually clears within 10 days. Other adverse effects include temporary dyspigmentation and very rarely scarring, vesiculation, and crusting that usually fade within a few weeks.¹⁴

The 532nm laser and 1064nm wavelength lasers are currently being used in an off-label manner by [name] of UCF Health to treat patients with cutaneous lupus with excellent clinical results. As there is limited data on the use of the 532nm and 1064nm lasers for cutaneous lupus, we hope to quantify the magnitude of the results in a prospective manner.

As lasers with these wavelengths are present in many dermatology practices, we hope that data from this study will educate and encourage more providers to use lasers, such as the one in this study, to benefit their patients with cutaneous lupus.

5) Setting of the Human Research

- The human research will be conducted at UCF Health Clinic at [name].
- UCF College of Medicine's resources will be used during data analysis
- We have obtained permission and approval from UCF Health medical director [name]

6) Resources available to conduct the Human Research

- Participants will be recruited through the UCF Health Clinic, Lupus Foundation of Florida, and the Central Florida Society of Dermatology. This represents a large pool of potential participants from which to recruit.
- The study's small sample size (N=25) makes it likely that the required number of participants will be recruited in less than 12 months.

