- Research will be conducted during [name] clinical time. [name], a UCF Health board-certified physician, will perform the screening of eligible participants. [name] has significant prior experience conducting research, knowledge of the regulations and customs at UCF Health, and works regularly with patients performing laser treatments. Off-label laser treatments currently performed are fractionated CO2 laser for morphea, 1064nm and 532nm laser for sarcoidosis and acne, and 532nm laser for cutaneous lupus among others. Experience has been presented at invited talks/grand rounds. All treatments will be administered by [name].
- All individuals assisting in the research study will be provided a copy of the approved IRB study protocol and given the opportunity to meet with the principal investigator before recruitment begins. The principal investigator, [name], will be responsible for informing all research staff of their research-related duties during a personal meeting or via phone or email. The contact information of the principal investigator and co-principal investigators will be distributed to all research staff and the participants.

- The study will be conducted at the UCF Health Clinic, see section 5 (Setting of the Human Research). Extramural funding will be sought from various organizations or industry.
- The chances of a research related injury are extremely rare. However treatment for research related minor injuries will be made available at no cost by [name] if possible. For injuries that cannot be treated by [name] the participant will be referred elsewhere. Costs associated with this treatment may be billed to the participant's insurance company. Costs not covered by participant's insurance company will be the participant's responsibility.
- The study has been approved by the UCF Health Privacy Officer.

7) Study Design

a) Recruitment Methods

- For this study, we will recruit 25 adult male and female volunteers age 18 years and older. This number was calculated with the University of California San Francisco (UCSF) Clinical and Translational Science Institute Sample Size Calculator with a power of 0.8, effect size of 0.25, and alpha of 0.05.

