- Participants with a diagnosis of cutaneous lupus will be recruited from the UCF Health Clinic during a patient's visit (medical records will not be searched for patients with a diagnosis of cutaneous lupus) and through advertising on the UCF Health website and within the UCF Health clinic. Potential participants also will be identified through email by the Lupus Foundation of Florida to its membership and the Central Florida Society for Dermatology. (See attached "Advertisement").
- [name] and [name] will rely on prior labs, pathology reports, and physical examination to determine if the participant has cutaneous lupus.
- If interested in participating, participants will contact the primary or co-investigator, who will provide instructions on how to enroll in the study.
- The investigator will describe the details of the study and answer any questions the participant may have about the study. Participants will be given an informed consent about the study and the primary investigator's contact information. Those participants who express interest in the study will be required to sign the HIPAA Authorization form (attached), Informed Consent form (attached) to ensure that there is no coercion in the study. Each of these will be signed both by the participant and by [name].

b) Participant Compensation

- The study participants will not be receiving any compensation for their participation in the study.

c) Inclusion and Exclusion Criteria

- For this study, we will recruit approximately 25 male and female volunteers ages 18 and older. All volunteers will be asked to give informed consent and sign a

HIPAA authorization before participation in the experiment. Participants will be screened in person before the research takes place. Participants will be screened and evaluated in the clinic to verify diagnosis through history, physical findings, health records, and previous labs. Participants who fit the diagnosis of cutaneous lupus will be asked whether they wish to participate in the study during the patient visit.

- Inclusion Criteria:
 - Male or female adult 18 years of age or older
 - Ability to rate level of pain
 - Ability to rate visual satisfaction
 - At least 2 active lesions of CLE

- Exclusion Criteria:
 - New or change in systemic medication for cutaneous lupus in past 6 months
 - Allergy to triamcinolone or betamethasone dipropionate cream
 - Pregnancy
 - Currently a prisoner

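### Only one topical-only control lesion is scored per participant, and a third lesion in skin types IV-VI has no stated role; scoring a spare lesion as a second control is a cheap, modest gain in precision

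*Combined protocol and SAP*

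**What the plan says.** Section 7 f) (Procedures) describes a within-participant comparison: "One lesion will only receive topical treatment to serve as a control, and up to 2 others will also receive laser treatment". All study lesions also receive the topical steroid.

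Entry under section 7 c) requires "At least 2 active lesions of CLE". No upper limit and no expected distribution of lesion counts are given.

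For Fitzpatrick types I-III, one laser is chosen by coin flip for the treatment lesion, and a third lesion has a stated use: "If the participants have an additional lesion then this will be treated with the laser not used for the treatment lesion". For types IV-VI the text says "Treatment lesion will only be treated with the 1064nm laser" and has no rule for an additional lesion.

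On size, section 6 speaks of a "small sample size (N=25" participants), and section 7 a) derives this "with a power of 0.8, effect size of 0.25, and alpha of 0.05". Section 7 g) adds only that "A significance level of 0.05 will be used for statistical hypothesis testing". No test or model, standard deviation, or correlation between lesions of one participant is given.

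**The concern.** The main question is whether laser plus topical steroid does better than topical steroid alone, and each participant answers it with a difference between lesions. With one laser lesion and one control lesion, half of the lesion-level variance of that difference comes from the single control. In a type I-III participant who receives both lasers, the same control is the comparator for both wavelengths, so its error enters both contrasts.

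The laser side may expand when more lesions exist, but the control side may not. The rule for an additional lesion in types I-III shows that the authors foresaw participants with three or more lesions. In a trial of 25, a further lesion scored at visits that already take place adds information without more participants or laser exposure. As written, the plan does not collect it.

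**Working it through.** **The plan's own figure.** N=25 does not follow from an effect size of 0.25, power 0.8 and alpha 0.05 under the standard readings. As a paired standardized effect of 0.25, two-sided, the requirement is 128 pairs (noncentral t), and power at 25 pairs is 22.5%. The 80% used below is therefore a reference point and not the trial's actual power.

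**Inputs.** From the documents: 25 participants, one control lesion, alpha 0.05 (taken as two-sided). Assumed, because the documents give none of them:
- s², the residual variance of one lesion within a participant, equal and independent across lesions
- τ², the between-participant variance of the laser effect
- q, the share of participants with a spare lesion.

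**Variance of one participant's difference.** For one laser lesion minus the mean of c control lesions, Var = s²(1 + 1/c) + τ².
- τ² = 0: 2.0 s² with c = 1 and 1.5 s² with c = 2. The reduction is 0.5/2.0 = 25%.
- τ² = 0.5 s²: 2.5 s² falls to 2.0 s², which is 20%.
- τ² = s²: 3.0 s² falls to 2.5 s², which is 17%.

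**Across the trial.** The calculation lets all 25 participants contribute one laser-minus-control difference. A paired t test with 25 pairs has 80% power at a standardized effect of 0.584, which is 0.584 × √2 = 0.826 s when τ² = 0.

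With inverse-variance weighting and τ² = 0, information relative to the present design is (1 − q) + q × 2.0/1.5 = 1 + q/3. An unweighted paired test on each participant's mean control value gives 2/(2 − 0.5q). Noncentral-t power with 24 degrees of freedom:

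| Share with a spare, q | Equivalent N, weighted | Power, weighted | Power, unweighted | Power, weighted, τ² = 0.5 s² |
|---|---|---|---|---|
| 0% | 25.0 | 80.0% | 80.0% | 80.0% |
| 10% | 25.8 | 81.3% | 81.0% | 81.0% |
| 20% | 26.7 | 82.5% | 82.0% | 81.9% |
| 40% | 28.3 | 84.7% | 84.0% | 83.6% |
| 60% | 30.0 | 86.6% | 86.0% | 85.2% |

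The ceiling is q = 100% with τ² = 0: N equivalent to 33.3, a standard error 13.4% smaller, and power 89.9%. At a paired standardized effect of 0.25, that same ceiling only moves power from 22.5% to 28.3%.

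**Which contrasts can gain.**
- Exactly two lesions: no spare, so no gain.
- Types IV-VI, three lesions: the third could be a second control for 1064nm versus topical.
- Types I-III, three lesions: the third already goes to the other laser, so a spare needs a fourth. That fourth lesion is the only source of gain for 532nm versus topical, since 532nm is not used in types IV-VI. It would also lower the correlation between the two laser-minus-control contrasts from s²/(2.0 s²) = 0.50 to 0.5 s²/(1.5 s²) = 0.33 (τ² = 0).
- 532nm versus 1064nm in participants given both: the control cancels, so no gain.

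**The case against.** The strongest reply is that nothing here is wrong. One control against one or two laser lesions in the same person is a coherent design, it biases no estimate, and nearly any trial could be made less noisy by measuring more. That stands, and it is why this is offered as an improvement and not as a defect.

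A reader might infer that every laser-versus-topical contrast is weakened. The documents do not support that: two lesions suffice for entry, and a third lesion in types I-III is already used.

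A reader might also infer that a third lesion in types IV-VI is deliberately left out. That rests on silence. The general sentence allows up to two laser lesions and is not confined to types I-III, while the type IV-VI rule speaks of a single treatment lesion. What the text supports is an ambiguity that must be reconciled.

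The size of the gain rests on assumptions. At a 10% share, power moves by about one percentage point. The rule for additional lesions is conditional and does not show how many participants will have one.

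Nor should a poorly photographed control be given much weight. One assessor evaluates participants at the visits and a blinded observer evaluates photographs, so a bad image affects only the photograph-based score.

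What remains is that the plan caps the control side at one and gives further lesions in types IV-VI no stated use, although scoring one costs little.

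**Conclusion.** The point holds as a cheap and modest improvement. Where a spare lesion exists, a second topical-only control reduces the variance of that participant's laser-minus-control difference by 25% if the laser effect is constant across participants, and by 20% if that effect varies with variance 0.5 s². For the trial, a reference power of 80% becomes about 81% to 87% if 10% to 60% of participants have a spare. These figures assume equal and independent lesion errors, an unknown share with spares, and a reference effect that the documents do not state. The table also lets all 25 participants inform one contrast. Each wavelength's own contrast draws only on those who receive it, so its absolute power depends on the skin-type mix, which is not given either.

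The change should not be presented as a remedy for the sample size. Whatever the share with spares, N=25 remains unexplained by the stated inputs.

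**What to change.** 1. In section 7 f), change the control rule from one topical-only lesion to at least one.
2. In the same section, state what happens to a further active lesion in types IV-VI, and reconcile that with the general sentence allowing up to two laser lesions.
3. At Visit 1, before any treatment, designate up to one further lesion that is not assigned to laser as an additional topical-only control. It should be of the same lesion type as the first control, because the protocol assigns discoid and non-discoid lesions different steroids. Photograph and score it at Visits 1, 2 and 3. Participants without a spare are handled as now.
4. In section 7 g), name the analysis: a lesion-level mixed model with a participant effect. The participant's mean control value in a paired analysis is a simpler alternative with a slightly smaller gain (84.0% instead of 84.7% power at a 40% share).

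The cost is protocol wording plus one more set of photographs and one more four-item score per visit in participants with a spare lesion, for assessors already in place. No participants, visits or laser sessions are added.
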